9.4 Vital Sign Data

For each vital sign parameter (in the sitting position), descriptive statistics of actual measurements and changes from baseline at each time point and the last assessment time point will be calculated for each treatment group and for the overall brexpiprazole group.

Numbers and proportions of subjects with vital signs meeting the criteria for potentially clinically significant vital signs (Appendix 1) will be determined for each treatment group and for the overall brexpiprazole group. A listing of these subjects will be provided.

9.5 Physical Examination Data

Physical examination data will be provided in a listing.

9.6 Electrocardiogram Data

For heart rate, PR interval, RR interval, QRS interval, QT interval, and QT corrected for heart rate (QTc), descriptive statistics of actual measurements and changes from baseline at each time point and the last time point will be calculated for each treatment group and for the overall brexpiprazole group.

A shift table from baseline for normal/abnormal 12-lead electrocardiogram (ECG) (evaluated at the trial site) will be produced for each treatment group and for the overall brexpiprazole group.

Numbers and proportions of subjects with actual measurements of QTc (QTcF, QTcB, QTcN = QT interval/[RR interval]^{0.37}) not meeting the criteria of > 450 msec, > 480 msec, and > 500 msec at baseline and meeting the criteria after treatment and numbers and proportions of subjects with changes from baseline of > 30 msec and > 60 msec will be determined for each treatment group and for the overall brexpiprazole group. Numbers and proportions of subjects with actual measurements of > 450 msec with a % change from baseline of > 10% will be determined for each treatment group and for the overall brexpiprazole group.

Numbers and proportions of subjects with ECG results meeting the criteria for potentially clinically significant ECG data (Appendix 3) will be determined for each treatment group and for the overall brexpiprazole group. A listing of these subjects will be provided.

9.7 Other Safety Data

9.7.1 Body Weight and Body Mass Index

For body weight and BMI, descriptive statistics of actual measurements and changes from baseline at each time point and the last assessment time point will be calculated for each treatment group and for the overall brexpiprazole group.

In addition, analysis will be performed by the analysis of covariance (ANCOVA) model with treatment group, medical care category (inpatient or outpatient), and prior use of antipsychotics (yes or no) as factors and baseline as a covariate. Least square means of each treatment group and differences in least square means between each brexpiprazole group and the placebo group, as well as the two-sided 95% CIs will be determined.

Numbers and proportions of subjects with results meeting the criteria for potentially clinically significant body weight gain or loss (Appendix 1) will be determined for each treatment group and for the overall brexpiprazole group. Body weight data will also be analyzed by baseline BMI category ($< 18.5, \ge 18.5$ to $< 25, \ge 25$ to $< 30, \ge 30$) in a similar manner. A listing of subjects with results meeting the criteria for potentially clinically significant body weight gain or loss (Appendix 1) will be provided.

9.7.2 DIEPSS, AIMS, and BARS

For DIEPSS total score (total of scores for items 1 through 8) and score for each DIEPSS item, AIMS total score (total of scores for items 1 through 7) and score for each of the 3

global judgment items (items 8 through 10), and BARS, descriptive statistics of actual measurements and changes from baseline at each time point, at the last assessment time point, and for the worst postdose measurement, will be calculated for each treatment group and for the overall brexpiprazole group.

In addition, analysis will be performed by the ANCOVA model with treatment group, medical care category (hospitalized or outpatient), and prior use of antipsychotics (yes or no) as factors and baseline as a covariate. Least square means of each treatment group and differences in least square means between each brexpiprazole group and the placebo group, as well as the two-sided 95% CIs will be determined.

9.7.3 Sheehan Suicidality Tracking Scale

For the score for each S-STS item (2 through 14), total score, suicidal ideation subscale score, and suicidal behavior subscale score, descriptive statistics of actual measurements and changes from baseline at each time point and the last assessment time point will be calculated for each treatment group and for the overall brexpiprazole group.

In addition, analysis will be performed by the ANCOVA model with treatment group, medical care category (hospitalized or outpatient), and prior use of antipsychotics (yes or no) as factors and baseline as a covariate. Least square means of each treatment group and differences in least square means between each brexpiprazole group and the placebo group, as well as the two-sided 95% CIs will be determined.

10 Pharmacokinetic Analyses

Pharmacokinetic analysis will be performed on the pharmacokinetic analysis set.

Descriptive statistics of plasma brexpiprazole concentrations at time points (0-6, 6-12, 12-18, 18-24, 24-30 hours and > 30 hours) after the most recent dosing as well as trough brexpiprazole concentrations (20-28 hours after the most recent dosing) and plasma brexpiprazole concentrations at all time points will be calculated by treatment group. The descriptive statistics will also be calculated by CYP2D6 phenotype (EM, IM, PM, and Unknown) in each treatment group in the same manner.

The mean plasma brexpiprazole concentration over time will be plotted by treatment group. Plotted diagrams by CYP2D6 phenotype in each treatment group will also be provided in the same manner.

Scatter plots of plasma brexpiprazole concentrations will be provided by treatment group. Scatter plots by CYP2D6 phenotype in each treatment group will also be provided in the same manner.

Plasma brexpiprazole concentrations below the lower limit of quantitation will be handled as 0 (ng/mL) when their descriptive statistics are calculated and when plotted diagrams and scatter plots are created.

11 Pharmacodynamic Analyses

Not applicable.

12 Pharmacogenomic Analyses

CYP2D6 genotype (phenotype) will be tabulated as specified in Section 7.2. CYP2D6 phenotype will also be summarized in subgroup efficacy and safety analyses.

13 Analysis of Other Endpoints

Analysis of other endpoints will be performed using the safety analysis set. Baseline is defined as the last data obtained prior to initiation of IMP treatment.

- ADCS-ADL
- MMSE
- EQ-5D-5L

For ADCS-ADL total score, MMSE total score and each item of EQ-5D-5L (subject evaluation [proxy version] and caregiver evaluation), descriptive statistics of actual measurements and changes from baseline at each time point and the last assessment time point will be calculated for each treatment group and for the overall brexpiprazole group.

In addition, analysis will be performed by the ANCOVA model with treatment group, medical care category (hospitalized or outpatient), and prior use of antipsychotics (yes or no) as factors and baseline as a covariate. Least square means of each treatment group and differences in least square means between each brexpiprazole group and the placebo group, as well as the two-sided 95% CIs will be determined.

14 Interim Analysis

Safety will be evaluated by the IDMC when approximately 25%, 50%, and 75% of the target number of subjects have completed or discontinued the trial.

A statistical analysis plan for interim analysis is described in a separate interim analysis plan.

15 Changes in the Planned Analyses

- In the subgroup efficacy analysis, "other" was excluded from the type of caregiver. The CMAI total score category at baseline was changed from "< 56 or ≥ 56 " to "< median or > median."
- The following changes were made to categorical analyses of QTc:
 Only subjects with postdose QTc meeting the criteria were summarized, instead of summarization at all time points.
 - Only subjects with QTc not meeting the criteria at baseline and meeting the criteria after baseline were summarized.
- It was decided that CYP2D6 phenotype would be tabulated as specified in Section 7.2. CYP2D6 phenotype were also summarized in subgroup efficacy and safety analyses.
- The original plan of using the LOCF dataset in ANCOVA of safety endpoints and other endpoints was changed as follows: Measurements at each time point and at the last assessment time point and, as necessary, the worst postdose measurement were included in the analysis.
- The original plan of calculating descriptive statistics of plasma brexpiprazole concentrations by treatment group in pharmacokinetic analysis was changed as follows: Descriptive statistics of plasma brexpiprazole concentrations at each time point after the most recent dosing, trough concentrations, and plasma drug concentrations at all time points were calculated by treatment group and by CYP2D6 phenotype in each treatment group. Additionally, the mean plasma brexpiprazole concentration over time and scatter plots of plasma brexpiprazole concentrations were provided by treatment group and by CYP2D6 phenotype in each treatment group.

16 References

C.S. Davis, Y. Chung. Randomization model methods for evaluating treatment efficacy in multicenter clinical trials. Biometrics. 1995; 51(3): 1163-1174.

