17	Patients meeting any of the following criteria at screening:Hypotension with symptoms
	• Orthostatic hypotension in which blood pressure after at least 3 minutes of standing is ≥ 30 mmHg lower for systolic blood pressure (SBP) or ≥20 mmHg lower for DBP compared with pressures in the supine position before standing
18	Patients with the following abnormal laboratory test values at screening (assessed on the basis of the results from the central laboratory):
	• Platelet count: $\leq 75,000/\text{mm}^3$
	• Hemoglobin: $\leq 9 \text{ g/dL}$
	• Neutrophil count: $\leq 1000/\text{mm}^3$
	• Aspartate aminotransferase (AST) and alanine aminotransferase (ALT): > 2 times the upper limit of normal (ULN)
	• Creatine phosphokinase (CPK): > 3 times ULN (however, this does not apply if the medical monitor judges that there will be no medically significant problems)
	• Albumin: $< 3 \text{ g/dL}$
19	Patients whose body weight at screening or baseline evaluation is < 30 kg

Protocol 331-102-00088

Tab	le 3.4.3-1 Exclusion Criteria
20	Patients whose Sheehan Suicidality Tracking Scale (S-STS) score at screening or baseline evaluation matches any of the following criteria or who are judged by the investigator or subinvestigator to be at high risk of suicide:
	• Patients with a score of 3 or 4 on any of S-STS Questions 2, 3, 4, 5, 6, or 11
	• Patients with a score of 2 or more on any of S-STS Questions 1a, 7, 8, 9, 10, or 12
21	 The following patients falling under the contraindications in the package insert for REXULTI[®]: Patients in a coma
	• Patients under the strong influence of central nervous system depressants, including barbiturate analogs/anesthetics
	Patients receiving adrenaline
	• Patients with a history of hypersensitivity to the components of REXULTI [®]
22	Patients with thyroid disease (not including patients whose condition has been kept stable via drug therapy for at least 3 months prior to the acquisition of informed consent) or patients who show
	abnormal values for thyroid-stimulating hormone (TSH) and free thyroxine (FT4) in the screening examination
23	Patients who are likely to require any prohibited medications during the trial period
24	Patients who have previously taken brexpiprazole

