6.6.5.3 S-STS

For each item of S-STS, descriptive statistics of actual measurements and changes from baseline at each time point will be calculated for each treatment group and for the overall brexpiprazole group.

In addition, using the LOCF data set, analysis will be performed by the ANCOVA model with treatment group, medical care category (hospitalized or outpatient), and prior use of antipsychotics (yes or no) as factors and baseline as a covariate. Least square means of each treatment group and differences in least square means between each brexpiprazole group and the placebo group, as well as the two-sided 95% CIs will be determined.

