3.5.8 Sheehan Suicidality Tracking Scale (S-STS)

The S-STS total score will be the sum of scores for Item 1a, Items 2 through 11, highest of Item 12 or any row of Item 16, highest of Item 14 or any row of Item 15, Item 17, and Item 20.

The S-STS suicidal ideation subscale score will be the sum of scores for Items 2 through 11.

The S-STS suicidal behavior subscale score will be the sum of scores for Item 1a, highest of Item 12 or any row of Item 16, highest of Item 14 or any row of Item 15, Item 17, and Item 20.

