CT-10.5.1	Incidence of Laboratory Test Values With Potential Clinical Relevance - Prolactin
	(Safety Analysis Set)
CT-10.5.2	Listing of Laboratory Test Values With Potential Clinical Relevance - Prolactin
CT 10.61	(Safety Analysis Set)
CT-10.6.1	Incidence of Treatment-emergent Significant Change in Lipids (Safety Analysis Set)
CT-10.6.2	Listing of Treatment-emergent Significant Change in Lipids (Safety Analysis Set)
CT-10.7.1	Incidence of Treatment-emergent Significant Change in Glucose (Safety Analysis
01 101/11	Set)
CT-10.7.2	Listing of Treatment-emergent Significant Change in Glucose (Safety Analysis Set)
CT-11.1	Mean Change From Baseline in Vital Signs (Safety Analysis Set)
CT-11.2	Incidence of Potentially Clinically Relevant Abnormalities in Vital Signs (Safety
OT 11.2	Analysis Set)
CT-11.3	Listing of Potentially Clinically Relevant Abnormalities in Vital Signs (Safety
CT-11.4	Analysis Set) Summary of Mean Change From Baseline to Double Blind Treatment Period by
	Study Week in Body Weight (kg) (Safety Analysis Set)

CT-11.5	Summary of Mean Change From Baseline to Double Blind Treatment Period by
CT-11.6	Study Week in BMI (kg/m^2) (Safety Analysis Set) Incidence of Potentially Clinically Relevant Weight Gain or Loss by Baseline BMI
	(Safety Analysis Set)
CT-12.1	Mean Change From Baseline in ECG Results (Safety Analysis Set)
CT-12.2	Shift Tables of ECG (Safety Analysis Set)
CT-12.3	Incidence of Categorical Increases in QT Evaluations (Safety Analysis Set)
CT-12.4	Incidence of Potentially Clinically Relevant Abnormalities in ECG
	Evaluations (Safety Analysis Set)
CT-12.5	Listing of Potentially Clinically Relevant Abnormalities in ECG Evaluations (Safety
	Analysis Set)
CT-13.1	Summary of Mean Change From Baseline to Double Blind Treatment Period by
CIT. 12.2	Study Week in DIEPSS (Safety Analysis Set)
CT-13.2	Summary of Mean Change From Baseline to Double Blind Treatment Period by
CT-13.3	Study Week in AIMS Total Score and Item Scores 8, 9 and 10 (Safety Analysis Set) Summary of Mean Change From Baseline to Double Blind Treatment Period by
C1-13.3	Study Week in BARS, Global Clinical Assessment of Akathisia (Safety Analysis
	Set)
CT-14.1	Summary of Mean Change From Baseline to Double Blind Treatment Period by
	Study Week in Sheehan-STS Score (Safety Analysis Set)
CT-14.2	Summary of Mean Change From Baseline to Double Blind Treatment Period by
	Study Week in Sheehan-STS - Total Score (Safety Analysis Set)

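### The SAP plans no count of subjects whose suicidal ideation or behaviour emerges or worsens on the S-STS; only suicidality reported as an adverse event is counted.

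*SAP*

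**What the plan says.** Protocol 6.6.5.3 plans the S-STS analysis as "For each item of S-STS, descriptive statistics of actual measurements and changes from baseline at each time point will be calculated", plus an ANCOVA on the LOCF data. SAP 9.7.3 keeps that form: "For the score for each S-STS item (2 through 14), total score, suicidal ideation subscale score, and suicidal behavior subscale score, descriptive statistics" at each time point and at the last assessment, and then "In addition, analysis will be performed by the ANCOVA model with treatment group, medical care category (hospitalized or outpatient), and prior use of antipsychotics" as factors, with baseline as covariate. The four S-STS tables in SAP Appendix 5 (CT-14.1 to CT-14.4) cover the item scores, the total and the two subscales. All are titled as summaries of mean change.

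Three other places bear on the point.

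- **Scoring.** In SAP 3.5.8, "The S-STS suicidal behavior subscale score will be the sum of scores for Item 1a", to which are added the higher of item 12 and the item 16 rows, the higher of item 14 and the item 15 rows, item 17 and item 20.
- **Entry limits.** Protocol 3.4.3, criterion 20, reads the scale by thresholds. It excludes scores of 3 or 4 on items 2 to 6 and 11, and also "Patients with a score of 2 or more on any of S-STS Questions 1a, 7, 8, 9, 10, or 12".
- **Adverse events.** SAP 9.2.1 counts subjects with suicide-related adverse events by arm and for pooled brexpiprazole. Appendix 4 includes ideation, behaviour and attempt terms. CT-8.9.17 is the incidence table and CT-9.4.17 the listing.

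**The concern.** The safety question for a suicidality scale is how many subjects developed or worsened in ideation or behaviour on treatment, and how that compares with placebo. A mean change does not answer it. If few subjects are affected, the mean moves by hundredths of a point, which has no clinical reading, and a maximum shows that a high score occurred but not in how many subjects.

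The SAP counts subjects meeting criteria for laboratory values, prolactin, vital signs, QTc and body weight. For DIEPSS, AIMS and BARS it also summarises change at the last assessment "and for the worst postdose measurement". SAP 9.7.3 has neither a count nor a worst value. What is at stake is whether the structured suicidality instrument yields a result that a reader of the study report can use without working through subject listings.

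**Working it through.** The documents give no figure on this point, so there is none to reproduce. The check sets passages side by side and then adds an illustration on assumed data.

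**1. Is anything counted from the S-STS?** Protocol 6.6.5.3, SAP 9.7.3 and CT-14.1 to CT-14.4 contain no incidence, shift or threshold table. Item-level S-STS data appear by subject in PDATA-11.1 to 11.3.

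**2. Does the adverse-event count stand in for it?** In part. Protocol 5.2 elicits adverse events with one open question about how the subject has felt, in patients with MMSE 1 to 22 (inclusion criterion 6). Protocol 3.8.3.8.4 has the investigator complete 22 structured questions. No rule was found linking a positive answer to an adverse-event entry.

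**3. Can the ever-affected number be recovered from the rows by time point?** No. After baseline the scale is scheduled at Week 4 and at Week 10 or discontinuation (Protocol Table 3.8-1), and each rating covers only the time since the previous visit. An event rated at Week 4 can be zero at the last assessment. Even if each row gave a count, the number ever affected could lie anywhere from the larger of the two to their sum.

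**4. Item range.** The protocol promises each item; SAP 9.7.3 summarises items 2 to 14. Items 1a, 15, 16, 17 and 20 feed the behaviour and total scores (SAP 3.5.8) but have no item summary outside the listings. SAP section 15 does not record the change.

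**5. Illustration.** The planned arm size is 148 on 2 mg and 148 on placebo. The counts and scores are assumptions, with every other subject at zero throughout. With k emergent subjects at score s, the mean difference is k × s / 148.

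| Emergent on 2 mg | Score | Mean difference | Count |
|---|---|---|---|
| 1 | 3 | 1 × 3 / 148 = 0.020 | 1/148 = 0.7% |
| 3 | 2 | 3 × 2 / 148 = 0.041 | 3/148 = 2.0% |
| 3 | 4 | 3 × 4 / 148 = 0.081 | 3/148 = 2.0% |
| 5 | 3 | 5 × 3 / 148 = 0.101 | 5/148 = 3.4% |

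The Clopper-Pearson 95% interval for 3/148 is 0.42% to 5.81%.

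**6. Does improvement elsewhere cancel the signal?** Take three emergent subjects at score 2 and three others on 2 mg falling from 2 to 0. The 2 mg mean change is (3 × 2 − 3 × 2) / 148 = 0. An ANCOVA with treatment and baseline only still gives a between-arm difference of 0.041, the same as without the improvers. The cancellation is in the within-arm mean, not in the adjusted comparison.

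**The case against.** The case against is substantial, and most of it limits how far the point goes.

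- **Suicidality is counted.** A reader might infer from SAP 9.7.3 that emergent suicidality goes uncounted altogether. The documents do not support that: SAP 9.2.1, Appendix 4 and CT-8.9.17 count it by arm when it is reported as an adverse event. The S-STS rater is the investigator or subinvestigator, who also reports adverse events, so the two sources probably overlap. How far is unknown.
- **Emergent cases do not average out between arms.** Step 6 shows that the planned baseline adjustment keeps the difference.
- **Week 4 is not lost.** It has its own row, and SAP 7.2 defines descriptive statistics to include the maximum. SAP section 15 also allows a worst postdose value in the safety ANCOVAs where necessary, though 9.7.3 names none.
- **Near-zero baselines are an inference.** Criterion 20's score limits alone allow up to 2 on six ideation items and 1 on four, so an ideation subscale of 6 × 2 + 4 × 1 = 16 at entry. No baseline distribution is given.
- **Counts do not detect more.** For 3 against 0 the t-test gives p = 0.08 and Fisher's exact test p = 0.25; for 5 against 0 the values are 0.02 and 0.06. A count also treats a one-point rise and a large one alike.
- **Items 15 and 16 have several rows**, so there is no single item score to average, and both are listed by subject.

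What stands is that no aggregate S-STS figure says how many subjects were affected, and the item range was narrowed without a record.

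**Conclusion.** The point holds as a reporting gap. The S-STS is analysed by descriptive statistics and ANCOVA alone, and an S-STS signal not also reported as an adverse event would show only as a small mean, a maximum or a listing entry. In the illustration, one to five subjects newly scoring 3 correspond to a mean difference of 0.020 to 0.101 points, against a readable 0.7% to 3.4% of the arm. Those figures rest on assumed counts and scores at the planned arm size. The conclusion rests on the text and on the absence, as far as the documents show, of a rule turning a positive S-STS answer into an adverse event.

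The unrecorded move from every item to items 2 to 14 is a separate, smaller discrepancy between protocol and SAP. Neither issue touches the efficacy analysis. The case for change is that a count can be interpreted and the data are already collected; it is not a case about power.

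**What to change.** In SAP 9.7.3, add one incidence table beside CT-8.9.17, by arm and for pooled brexpiprazole. It should give the number and proportion of subjects:

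- whose worst on-treatment ideation subscale score exceeds baseline;
- whose worst on-treatment behaviour subscale score exceeds baseline;
- who have any post-baseline behaviour score above 0.

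Give exact 95% confidence intervals for the differences from placebo. Summarise items 1a, 15 to 17 and 20 as counts of subjects. Either restore the protocol's item coverage or record the narrower range in SAP section 15. The planned item-level ANCOVAs can stay.

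The cost is a paragraph of SAP text and one or two tables, with no new data collection. The drawback is sparse counts with wide intervals, so the table should be read as description.

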Appendix 1 Criteria for Identifying Vital Signs and Weight of Potential Clinical Relevance

Variable	Criterion Value ^a	Change Relative to Baseline ^a
Pulse Rate	> 120 bpm	≥ 15 bpm increase
Pulse Rate	< 50 bpm	≥ 15 bpm decrease
Systolic Blood Pressure	> 180 mmHg	≥ 20 mmHg increase
Systolic Blood Flessure	< 90 mmHg	≥ 20 mmHg decrease
Diastolic Blood Pressure	> 105 mmHg	≥ 15 mmHg increase
Diastolic Blood Pressure	< 50 mmHg	≥ 15 mmHg decrease
Waight		≥ 7% increase
Weight	-	≥ 7% decrease

^aIn order to be identified as potentially clinically relevant, an on-treatment value must meet the "Criterion Value" and also represent a change from the subject's baseline value of at least the magnitude shown in the "Change Relative to Baseline" column.

